11 SAFETY

11.1 DEFINITIONS

11.1.1 ADVERSE EVENT (AE)

An AE is any untoward medical occurrence in a subject administered a pharmaceutical product and does not necessarily have a causal relationship with this treatment. An AE can therefore be any unfavourable or unintended sign or symptom, intercurrent illness, injury, or any concomitant impairment of the subject's health, temporally associated with the use of a medicinal product, whether or not considered related to the medicinal product.

A treatment-emergent AE is any AE temporally associated with the use of a study drug, whether or not considered related to the study drug.

AEs include:

- Exacerbation of a chronic or intermittent pre-existing condition/disease/symptom
 present at baseline that worsen during the study including either an increase in
 frequency and/or intensity.
- Disease or medical condition detected or diagnosed after study drug administration even though it may have been present prior to the start of the study.
- Events considered by the Investigator to be related to study-mandated procedures.
- Abnormal safety assessments, e.g. laboratory test abnormalities, physical exam findings or vital sign measurements must be reported as AEs if they represent a clinically significant finding in the medical and scientific judgment of the Investigator, symptomatic or not, which was not present at baseline or if present at baseline, worsened during the course of the study or led to dose reduction, interruption or permanent discontinuation of study drug. However, if an abnormal laboratory or other safety-related test result is associated with clinical signs or symptoms, the signs or symptoms should be recorded as an AE. If signs and symptoms are part of a diagnosis, then the diagnosis should be recorded as AE.
- Signs, symptoms of a suspected drug interaction.
- Signs, symptoms of a suspected overdose of either the study drug or a concomitant medication (overdose per se will not be reported as AE/SAE).

AEs do not include:

• Medical or surgical procedure, e.g., surgery, appendectomy, endoscopy, tooth extraction, transfusion (as these are treatments for an AE). However, the event resulting in the procedure is the AE (e.g. appendicitis, abdominal pain).

CONFIDENTIAL Page 65 of 80

- Pre-existing disease or medical condition documented at baseline that does not worsen.
- Situations in which an adverse change did not occur, e.g., hospitalisations for cosmetic elective surgery or for social and/or convenience reasons.
- Anticipated day-to-day fluctuations or seasonal fluctuations (e.g. allergic rhinitis) of pre-existing disease(s) or condition(s) documented at baseline.
- The disease/disorder being studied, or the expected progression, signs or symptoms (including laboratory values) of the disease/disorder being studied, unless it is more severe than expected for the subject's condition.
- Overdose of either study drug or concomitant medication without any signs or symptoms.

11.1.2 SERIOUS ADVERSE EVENT (SAE)

An SAE is any untoward medical occurrence between the time of consent and the subject's final visit that:

- is fatal,
- is life-threatening,
- requires inpatient hospitalisation or prolongation of existing hospitalisation,
- results in persistent or significant disability/incapacity,
- results in a congenital anomaly/birth defect or
- is otherwise judged as medically significant (may jeopardise the subject).

The following guidelines should be used:

Life-threatening: Refers to an event in which the subject was at risk of death at the time of the event; it does not refer to an event which hypothetically might have caused death if it were more severe.

Inpatient hospitalisation: Subject has to stay in hospital at least overnight. The following reasons for hospitalisations are not considered AEs, and therefore not SAEs:

- Hospitalisations for cosmetic elective surgery, social and/or convenience reasons.
 Standard monitoring of a pre-existing disease or medical condition that did not worsen, e.g., hospitalisation for coronary angiography in a subject with stable angina pectoris.
- Elective treatment of a pre-existing disease or medical condition that did not worsen, e.g., hospitalisation for chemotherapy for cancer, elective hip replacement for arthritis, vein stripping for preventive and/or cosmetic purpose.

CONFIDENTIAL Page 66 of 80

Prolongation of hospitalisation: Complications that occur during hospitalisation are AEs. However, if a complication prolongs hospitalisation or would have required hospitalisation or fulfils any other serious criteria, that complication is considered an SAE. In any case, admission to an intensive care unit is considered a prolongation of hospitalisation. When in doubt as to whether "prolongation of hospitalisation" was necessary, the AE should be considered serious.

Significant disability: The term significant disability means that there is a substantial disruption of a person's ability to conduct normal life functions. This definition is not intended to include experiences of relatively minor medical significance such as uncomplicated headache, nausea, vomiting, accidental trauma (e.g. sprained ankle) or uncomplicated chronic diseases which may interfere or prevent everyday life functions but do not constitute a substantial disruption.

Medically significant: Medical and scientific judgment should be exercised in deciding whether other situations should be considered serious such as important medical events that might not be immediately life-threatening or result in death or hospitalisation but might/may jeopardise the subject or might/may require intervention to prevent one of the other outcomes listed in the definition above. Examples of such events are invasive or malignant cancers, intensive treatment in an emergency room or at home for allergic bronchospasm, blood dyscrasias or convulsions that do not result in hospitalisation, or development of drug dependency or drug abuse.

SAE related to study-mandated procedures: Such SAEs are defined as SAEs that appear to have a reasonable possibility of causal relationship (i.e., a relationship cannot be ruled out) to study-mandated procedures (excluding administration of study drug) or complication of a mandated invasive procedure (e.g., blood sampling, heart catheterisation), or car accident on the way to the hospital for a study visit, etc.

11.2 REPORTING AND DOCUMENTATION

AEs should be documented in terms of a medical diagnosis. When this is not possible, the AE should be documented in terms of signs and/or symptoms observed by the Investigator or reported by the subject at each study visit.

Any pre-existing conditions or signs and/or symptoms present in a subject prior to the start of the study should be recorded on the Medical History CRF.

All SAEs that occur after informed consent through to study completion (Follow-up visit) or premature discontinuation must be reported on the SAE form in the CRF and reported within 24 hours to the Sponsor using the Shield SAE form. All AEs occurring from the time of the first dose of study treatment through study completion (Follow-up visit) or premature

CONFIDENTIAL Page 67 of 80

discontinuation must be reported on the AE form in the CRF. For AEs related to COVID-19 testing, see section 10.1.

Any SAE that occurs during the clinical study or within two weeks of receiving the last dose of study drug, whether or not related to the study drug, must be reported to the Sponsor.

Deaths or congenital abnormalities if brought to the attention of the Investigator AT ANY TIME after cessation of study drug AND considered by the Investigator to be possibly related to study drug, should be reported to the Sponsor.

At each visit AEs will be solicited. The nature of each event should be established. Details of changes to study drug dosing or any subsequent treatment should be recorded on the appropriate pages of the CRF.

AEs already documented in the CRF (i.e., at a previous assessment) and designated as 'ongoing' should be reviewed at subsequent visits as necessary. Upon resolution, the date of resolution should be recorded in the CRF. If an AE increases in frequency or severity during a study period, a new record of the event should be started. If the AE lessens in intensity, no change in the intensity is required as only the worst intensity must be reported.

All AEs and SAEs, including those that are ongoing at the end of the study or at premature discontinuation, will be followed up until resolution or stabilisation or until the event is otherwise explained.

11.2.1 Immediate Reporting

The following AEs must be reported within 24 hours to the Sponsor or designee:

- SAEs
- Pregnancy (not considered as an AE, but must be reported immediately)

For immediate reporting, the Investigator must fill out the SAE form or the Pregnancy form for pregnancies and send to the Sponsor within 24 hours after awareness.

SAFETY CONTACT DETAILS

Primevigilance Limited has been contracted by the Sponsor for safety reporting

Email SAE reports to [contact] or fax to [contact]

Contact details for safety questions will be provided in the Investigator Site File

If the site obtains relevant follow-up information, this information needs to be forwarded to the Sponsor within 24 h of awareness using a new SAE form.

CONFIDENTIAL Page 68 of 80

Other documents must be submitted upon request. All documents must be blinded with respect to the subject's personal identification to meet data protection requirements, e.g., on the discharge summary this data must be blinded, and the subject number added.

As soon as the Sponsor is informed about an SAE, an evaluation and potential reporting to central IRBs/IECs, Competent Authorities (CA) and other concerned parties will occur as required. The Investigator will be responsible for reporting to any local IRB/IEC as required.

11.2.2 Non-Immediate Reporting

AEs that do not qualify for immediate reporting will be documented in the eCRF and reported in the Clinical Study Report (CSR).

11.3 EVALUATION

AEs and the corresponding entries in the eCRF will be reviewed by the Investigator or qualified member of the study staff. Adverse events, toxicities and medical surgery/history will be categorized by primary system organ class (SOC) and preferred term using the MedDRA dictionary. Toxicities will also be graded as mild, moderate or severe.

11.3.1 Intensity

The intensity will be rated by the Investigator as "mild", "moderate" or "severe":

Mild: Symptoms barely noticeable to the subject or does not make the subject uncomfortable; does not influence performance or functioning.

Moderate: Symptoms of a sufficient severity to make the subject uncomfortable; performance of daily activity is influenced; subject is able to continue in study.

Severe: Symptoms cause significant discomfort; incapacitation or significant impact on the subject's daily life; may cause cessation of study treatment.

A mild, moderate or severe AE may or may not be serious. These terms are used to describe the intensity of a specific event (as in mild, moderate, or severe myocardial infarction). A severe event may be of relatively minor medical significance (such as severe headache) and is not necessarily serious. For example, nausea lasting several hours may be rated as severe, but may not meet the definition of seriousness. Fever of 39 °C that is not considered severe may become serious if it prolongs hospitalisation.

11.3.2 Causality

The following should be considered when evaluating the relationship of AEs and SAEs to the study treatment:

Not related: There is not a possibility that the event has been caused by the product under investigation. Consideration should be given to factors, including but not limited to, a lack of reasonable temporal relationship between administration of the drug and the event, the

CONFIDENTIAL Page 69 of 80

presence of a biologically implausible relationship between the product and the AE (e.g. the event occurred before administration of drug), or the presence of a more likely alternative explanation for the AE.

Related: There is a possibility that the event may have been caused by the product under investigation. Consideration should be given to factors, including but not limited to a positive re-challenge, a reasonable temporal sequence between administration of the drug and the event, a known response pattern of the suspected drug, improvement following discontinuation or dose reduction, a biologically plausible relationship between the drug and the AE or a lack of an alternative explanation for the AE.

11.3.3 Outcome

The outcome of each AE has to be assessed as follows:

- Fatal: The AE resulted in death ("Death" is recorded as an outcome, not as the AE)
- Ongoing/Not resolved: The AE has not resolved
- Recovered with sequelae: Resolution of the AE has occurred, but the subject retains some sequelae
- Recovered: The AE fully resolved with no observable residual effects
- Unknown: The outcome of the AE is not known as the subject did not return for follow-up and attempts to locate the subject and/or to obtain follow-up information were unsuccessful (lost to follow-up).

11.4 RE-EXPOSURE

If an AE requires discontinuation of IMP and is judged to be treatment-related by the Investigator or by the Sponsor, re-exposure is not allowed. If an AE requires dose reduction or discontinuation of IMP and is judged by the Investigator or by the Sponsor to be unrelated to investigational products, the decision to re-introduce the medication or to increase the dose of the medication requires prior approval of the Sponsor or designee.

CONFIDENTIAL Page 70 of 80

12 STATISTICAL CONSIDERATIONS

12.1 POWER CALCULATIONS

The study will be analysed by descriptive statistics only. As such, there is no formal power calculation.

The aim is to recruit up to 49 subjects in each treatment group in the 2-17 years cohort. At least 12 subjects in each age group (i.e. 36 subjects in total) will be included in the PK model in the ferric maltol oral suspension group. A sample size of 49 in the Ferric Maltol group provides at least 80% power to demonstrate that the lower bound of the 95% confidence interval for increase in Hb at 12 weeks, compared with baseline, is above zero. This assumes that the SD of the change from baseline is 1.2 g/dL or lower and the true mean change is at least 0.5 g/dL.

Every effort will be made to recruit up to 12 subjects in the under 2's age group but in case of reasons of feasibility it cannot be completed, then the study may be completed without that cohort.

If less than 91 subjects in total have been randomized when 32 ferric maltol subjects have completed, then an interim analysis of the primary effectiveness endpoint (change in Hb concentration from baseline to Week 12) will be conducted. Less than 91 subjects recruited would indicate that the study will not complete in the near future.

The interim analysis will test for significance of the increase in Hb in the ferric maltol arm (from Baseline to Week 12). If significant, the study will stop recruitment. If not significant, the study will continue (all subjects will be assigned to ferric maltol) until 54 subjects have been recruited in the ferric maltol arm.

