In the Phase 1 paediatric PK study, children and adolescents aged 10 to 17 years were administered up to the adult dose of 30 mg BID. Given physiological control of intestinal absorption of iron uptake through the hepcidin pathway and considering a total daily dose of 60 mg iron is within the approved dosage regimen for oral ferrous products in older children, iron overload in a 10-day exposure was considered not to be a risk. Furthermore, in children the metabolism of maltol through glucuronidation in the liver was similar to adults. There was not any great individual clinical benefit over 10 days of ferric maltol therapy, although the information gathered was very important in establishing the doses to be studied in this subsequent Phase 3 paediatric efficacy and safety study in IDA subjects.

Doses chosen for this phase 3 study were based on the first Paediatric PK study and a new age-appropriate formulation has been developed. The study population will recruit subjects with iron deficiency anaemia who are otherwise generally well. The study population will include both female and male subjects aged 1 month - 17 years age range.

From the Phase I PK adult study comparing the ferric maltol suspension and ferric maltol capsule under fed and fasted condition, information was gathered that in the fed condition, ferric maltol capsule and suspension had similar PK with respect to serum iron C_{max} and AUC_{last} .

The C_{max} data suggest that there might be a formulation effect in the fasted state in favor of the capsule with respect to serum iron levels but this was not definitively supported by AUC_{last} and AUC_{inf} comparisons, nor was this supported by the maltol and maltol glucuronide PK.

Ferric maltol suspension had similar PK when administered in fasted or fed conditions with respect to Cmax and AUClast. Nevertheless, we advise ferric maltol should be taken at least 30 mins after meal.

PK assessments will take place for the first 12 subjects in age group 2 yrs -17 yrs) and all 1 m - < 2 yrs assigned to ferric maltol to assess the efficacy, the safety and tolerability of ferric maltol.

This study's procedures risks are related to IV cannulation and blood sampling, with fainting, minor bleeding and bruising regarded as the main risks. Total blood loss as a result of phlebotomy will be approximately 33.8 ml in subject group 1 m to less than 2 years and 40 ml in the 2 to 17 yrs age group.

CONFIDENTIAL Page 37 of 80

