Subjects aged 2-17 will be randomised 1:1 to receive ferric maltol oral suspension or ferrous sulfate oral liquid. The first 12 subjects randomised to ferric maltol in each age sub-groups (2 – 9 yrs, 10 – 17 yrs, respectively) will enter a Pharmacokinetic phase from Visit 2 (PK Day 1) till Visit 3 (PK Day 2) with 2 PK days. Following baseline pre-dose blood sample, subjects will take a single dose of 2.5 ml (2 yrs -11 yrs) or 5 ml (12 yrs - 17 yrs) ferric maltol oral suspension under supervision and then a further 2 PK blood samples will be taken up to 6 hours. Following the last scheduled PK sample on PK Day 1 (Visit 2), subjects will be reminded to take their dose twice daily until PK Day 2 (between Day 7-Day 10). On PK Day 2 (Visit 3) subjects should withhold their morning dose until attending their second PK assessment day. Same procedure will be repeated for PK assessment as on PK Day 1. Following PK Day 2, subjects will continue treatment until Week 12.

Once the 12 subjects in each age subgroup (2 - 9 yrs, 10-17 yrs, respectively) have finished their PK visits, they will continue on treatment until week 12. Further subjects will not need to have PK samples taken.

Subjects randomised to ferrous sulfate oral liquid will not need to complete the PK period, they will remain on oral ferrous sulfate until Week 12. Ferrous sulfate 125 mg/ml (25 mg/ml elemental iron) or equivalent dose will be used for all children/adolescents. To maximise the iron replenishment for subjects within this group as well; aged 2 - 17 yrs will be dosed 0.24ml (6mg elemental iron) per kg body weight, up to a maximum of 8ml given daily in two divided doses.

 Assigned treatment phase: 12 weeks open label treatment for ferric maltol children aged 1 month to less than 2 years

Once the PK samples have been analysed for subjects aged 1 month to less than 2 years and they can enrol in the randomisation phase, they will be assigned to receive ferric maltol oral suspension and start the 0.1 ml/kg/dose, BID on Visit 2 for 7-10 days. On Visit 3 (PK Day 2), following baseline pre-dose blood sample and urine sample, subjects will take a single dose of 0.1 ml/kg ferric maltol suspension under supervision and then a further three PK blood samples and urine samples will be taken at three timepoints up to 12 hours. Subjects will continue treatment until week 12.

- End of study: Week 12 visit

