10.2 DESIGN SCHEMATICS

 $^{^{1}}$: Only applicable if subjects aged 1 month to < 2 years continues to the assigned treatment phase.

²: Visit 3 will only be performed for the first 12 subjects in age group 2-17 years

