10.3 SCHEDULE OF ASSESSMENTS FOR SUBJECTS AGED 2 YEARS-17 YEARS

	SCREENING	TREATMENT					FOLLOW-UP
Duration	Up to 21 days	12 WEEKS (equivalent of 84 days)					10-14 days
Day		1	7-10	28	56	84	94-98
Visit ¹¹	1	2	3 ³	4	5	6	7 ^{9,10}
Informed Consent	х						
Eligibility ^{1,8}	х	х					
Demographics	х						
Medical History	х						
Physical Examination	х					х	
Vital Signs ²	х	х	Х	X	х	х	
Urine Pregnancy Test ⁴	х	х	х	х	х	х	
Clinical Laboratory tests ⁵	х					х	
Haematology ⁶	х			X		х	
Iron markers ⁶	х			Х		Х	
PK assessment PK Blood Sampling for maltol/maltol glucuronide and iron markers ⁷		х	х				
Randomisation ⁸		х					
Dispense Study Drug		х	х	х	х		
Return Study Drug for Accountability			х	х	х	х	
Palatability questionnaire		х		х			
Adverse Events		х	х	х	х	х	х
Concomitant Medications and Procedures	х	х	х	х	х	x	х
Compliance reminder		х	х	Х	х	х	
Compliance assessment			х	Х	х	Х	

CONFIDENTIAL Page 56 of 80

- 1. A subject may be retested once for laboratory criteria that do not meet protocol criteria so long as randomisation occurs no more than 21 days from the initial screening visit date (if eligible).
- 2. Vital Signs body weight, height, systolic/diastolic blood pressure, pulse, and body temperature at each visit. Patient weight should be recorded at each clinic visit and drug dosing administered as per last clinic visit weight.
- 3. Visit 3 (PK Day 2) only applicable for the first 12 subjects randomised to ferric maltol group in each age group (2 yrs -9 yrs, 10 yrs-17 yrs).
- 4. Urine pregnancy test for female subjects of childbearing potential only.
- 5. Clinical Laboratory tests including:
 - a. Clinical Chemistry: Vitamin B12, folate, ALT, AST, alkaline phosphatase, gamma-glutamyl transpeptidase (GGT), total bilirubin, creatinine, amylase, blood urea nitrogen (BUN), phosphorous, sodium, potassium, chloride, calcium, total cholesterol, uric acid, glucose, total protein, albumin
- 6. Haematology and Iron markers:
 - a. Haematology: Red blood cell count, haemaglobin, haematocrit, mean cell volume (MCV), white blood cell count (total and differential (% and absolute), absolute reticulocyte count and platelet count.
 - b. Iron Markers: serum iron, transferrin, transferrin saturation (TSAT), total and unsaturated iron binding capacity (TIBC, UIBC) and ferritin.

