2.2.4 Sample Size Determination

In total up to 110 patients will be recruited into the study. Up to 98 subjects will be randomised in the 2 -17 years cohort and up to 12 subjects will be assigned in the <2 years cohort.

The aim is to recruit up to 49 subjects in each treatment group in the 2 – 17 years cohort. At least 12 subjects in each age group respectively (i.e. 24 subjects in total) will be included in the PK analysis group in the ferric maltol oral suspension group. A sample size of 49 in the Ferric Maltol group provides at least 80% power to demonstrate that the lower bound of the 95% confidence interval for increase in Hb at 12 weeks, compared with baseline, is above zero. This assumed that the standard deviation (SD) of the change from baseline is 1.2 g/dL or lower and the true mean change is at least 0.5 g/dL.

Every effort will be made to recruit up to 12 subjects in the under 2's age group but in case of reasons of feasibility it cannot be completed, then the study may be completed without that cohort.

If less than 91 subjects in total have been randomised when 32 ferric maltol subjects have completed treatment (or withdrawn from the study), then an interim analysis of the primary effectiveness endpoint (change in Hb concentration from baseline to Week 12) will be conducted. If significant, the study will stop recruitment. If not significant, the study will continue (all subjects will be assigned to ferric maltol) until 54 subjects have been recruited in the ferric maltol arm.

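### Protocol 12.1 states a PK minimum of 36, but 36 is the most the design plans: 24 children aged 2–17 plus 0 to 12 infants, and other sections give different counts

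*Protocol*

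**What the plan says.** **Overall PK number.** Protocol 12.1: "At least 12 subjects in each age group (i.e. 36 subjects in total) will be included in the PK model". The same section aims for up to 12 infants and adds that, if recruiting them is not feasible, "then the study may be completed without that cohort". SAP 2.2.4 keeps that infant provision but gives a different total: "At least 12 subjects in each age group respectively (i.e. 24 subjects in total) will be included in the PK analysis group".

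**Ages 2–17, per age group.** Protocol 7.1: "The first 12 subjects randomised to ferric maltol in each age sub-groups (2 – 9 yrs, 10 – 17 yrs, respectively") enter the PK phase. Note 3 to the schedule of assessments (Protocol 10.3) limits Visit 3 to the same children: it is "for the first 12 subjects randomised to ferric maltol group in each age group". The synopsis, note 7 to 10.3, section 8.6.1, and SAP 2.2.1 and 3.5.1 agree.

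**Ages 2–17, as one group.** Protocol 5.6: "PK assessments will take place for the first 12 subjects in age group 2 yrs -17 yrs". The note under the 10.2 schematic: "Visit 3 will only be performed for the first 12 subjects in age group 2-17 years". Protocol 10.8.6 gives a blood volume for the first 12 ferric maltol subjects aged 2 to 17 years and does not split them by age group.

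**Infants.** The synopsis, 7.1 and 9.2 cap the infant cohort at 12. Section 9.2 applies the cap at entry to the pre-assignment phase, before the urine maltol result decides whether an infant goes on to treatment. The PK endpoint covers 1 month to 17 years (Protocol 6.4, SAP 2.3.2), and the SAP PK population (3.2.4) is not restricted by age.

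**The concern.** A minimum sample size should be one that the plan can meet when everything goes as permitted. A floor of 36 needs 12 infants, yet the section that sets the floor also allows none. The trial could follow the protocol in every respect and still report fewer PK subjects than the protocol says will be included at the least.

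The number also has a use. Protocol 9.3 lets the sponsor replace some discontinued subjects in order to reach an agreed number of evaluable PK subjects. With 36 in the protocol, 24 in the SAP and 12 in some passages on ages 2–17, that target is not defined.

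The wording on ages 2–17 bears on which children attend Visit 3 and have repeat blood sampling. The schematic note says that Visit 3 is for those first 12 only, which contradicts the schedule of assessments that follows it.

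**Working it through.** **1. The stated totals.** Each total reproduces on its own count of age groups.

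- Protocol 12.1: 3 groups × 12 = 36. This works only if infants are the third group.
- SAP 2.2.4: 2 groups × 12 = 24. This works only if the groups are 2–9 and 10–17 years.

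**2. The total the design plans.** Inputs: 12 in each of two age groups (Protocol 7.1, 10.3) and 0 to 12 infants (Protocol 12.1, 7.1). Planned total = 2 × 12 + infants.

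| Infants | Planned total |
|---|---|
| 0 | 24 |
| 3 | 27 |
| 6 | 30 |
| 9 | 33 |
| 12 | 36 |

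So 36 is reached only at the infant cap. The cap applies before the urine assessment, and infant blood PK is drawn only at Visit 3 (Protocol 10.4, note 6). The SAP PK population counts only randomised or assigned subjects. One infant not assigned to treatment therefore puts 36 out of reach on that definition.

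The 24 is a planned number of sampled children, not a guaranteed number of evaluable ones. The rule takes the first 12 per group, and the only slack is discretionary replacement under 9.3, which excludes discontinuations due to adverse events.

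**3. The two wordings for ages 2–17.**

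| Wording | Where | Number aged 2–17 |
|---|---|---|
| First 12 in each of 2–9 and 10–17 | Protocol synopsis, 7.1, 8.6.1, 10.3 notes 3 and 7; SAP 2.2.1, Table 2.1 note 3, 3.5.1 | 24 |
| First 12 aged 2–17 | Protocol 5.6, 10.2 schematic note, 10.8.6 | 12 |

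The sampling table in Protocol 10.8.2 has four schedules of 3 subjects, 4 × 3 = 12. It does not say whether that is per age group or overall, so it does not settle the question.

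**4. Size of the difference for ages 2–17.** Each schedule takes two post-dose samples:

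- Group 1: 0.5–1 h and 1–2 h
- Group 2: 0.5–1 h and 2–3 h
- Group 3: 1–2 h and 3–4 h
- Group 4: 2–3 h and 4–6 h

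| Window | 12 children (3 per schedule) | 24 children (6 per schedule) |
|---|---|---|
| 0.5–1 h | 6 | 12 |
| 1–2 h | 6 | 12 |
| 2–3 h | 6 | 12 |
| 3–4 h | 3 | 6 |
| 4–6 h | 3 | 6 |

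Standard error of a window mean = SD / √n. At equal SD, the ratio of 12 children to 24 is √(24/12) = √2 = 1.41 in every window. SAP 3.5.3 summarises ages 2–17 as one age group and SAP 3.5.4 pools them, so these are the relevant counts.

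**5. The haemoglobin power statement.** Inputs from Protocol 12.1: n = 49, SD 1.2 g/dL, mean change 0.5 g/dL. The standard error is 1.2/√49 = 0.171 and 0.5/0.171 = 2.917. Normal power is Φ(2.917 − 1.960) = 0.83; with the t distribution it is 0.82. Both agree with the stated 80% or more, and neither uses the PK number.

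**The case against.** The strongest reply is that this is loose wording. Neither total is a multiplication error, and they can be reconciled: the SAP sentence follows one about the 2–17 cohort and can be read as counting the two older groups, while the protocol adds the infants. SAP 3.5.4 derives PK parameters for ages 2–17 only, which fits 24. The paragraph after the 36 discloses that infants may be absent. The sections that govern assignment, visits and sampling all say 12 per age group, so the three short-form passages are probably shorthand. Section 5.6 is narrative, with an unmatched bracket in that sentence; the 10.2 schematic is not visible in the text available; and 10.8.6 gives a volume per child that does not depend on how many are sampled.

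Most of that stands. It limits three stronger conclusions that a reader might draw:

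- *Sites or the randomisation system would stop Visit 3 after 12 children.* That would mean disregarding the schedule of assessments and 8.6.1, and nothing in the documents ties the system to the schematic.
- *PK precision would fall by a factor of 1.41.* That holds only under the literal 12, and no precision target is stated for the PK summaries.
- *Omitting the infants costs a third of the PK information (12/36 = 33%).* Infants have their own sampling schedule, are summarised separately and do not enter the 2–17 parameters, so the results for ages 2–17 lose no precision.

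The reply does not remove the defect. Both sentences call their number a total and neither says whether infants are counted. The protocol sentence also follows one about ages 2–17, so position does not explain the difference. A disclosed option to omit the infants is incompatible with a minimum that requires all 12. The schematic note is still a literal contradiction about Visit 3.

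**Conclusion.** The point holds as an inconsistency in a stated sample size. Protocol 12.1 presents 36 as a minimum when it is the maximum of a planned range of 24 to 36. SAP 2.2.4 gives 24 as the total without saying that infants are left out. SAP section 5, which records changes to the haemoglobin analysis populations and the added Week 4 iron markers, does not mention it. Three protocol passages state 12 for ages 2–17 where the operative sections give 24.

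This rests on reading the per-age-group wording as the intended design, as most sections support, and on leaving aside discretionary replacement. The 1.41 ratio also assumes equal variability and applies only if the literal 12 were followed.

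The consequence is confined to PK planning and to a secondary, descriptive analysis (SAP 3.1.5). The haemoglobin endpoint is unaffected. It should be corrected because it sets the PK number and the replacement target, but it does not threaten the trial's main conclusions.

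**What to change.** 1. Restate Protocol 12.1 and SAP 2.2.4 in the same words: *24 subjects aged 2–17 (12 in each of 2–9 and 10–17 years) plus up to 12 infants if that cohort is enrolled (24 to 36 in total)*. Both need changing, because the SAP total omits infants who belong to its PK population.
2. Name this as the agreed PK number to which the replacement policy in Protocol 9.3 refers.
3. In Protocol 5.6, the 10.2 schematic note and 10.8.6, write *the first 12 ferric maltol subjects in each age group (2–9, 10–17)*.
4. If the protocol is not amended, list the difference between 36 and 24 in SAP section 5, so that the study report does not have to explain a PK count below a stated minimum.

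The cost is wording in one amendment or a SAP update. No assessment is added to those in the schedule of assessments. The downside is that the stated PK minimum falls from 36 to 24.
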